1.3 Rationale for conducting this study

The human absorption, metabolism, elimination study (TC-5214-23-CLP-002) has shown that the mean recovery of total radioactivity in urine was 96.1%. In urine, the individual total percent of dose corresponding to parent ranged from 89.5% to 93.9%. After oral administration, TC-5214 was systematically cleared by renal excretion mainly as unchanged drug and non-renal clearance was very minimal. Thus renal impairment is likely to significantly affect the PK of TC-5214. This study is being conducted as a standard approach to determine the effects of renal impairment and dialysis on the PK of TC-5214.

1.4 Benefit/risk and ethical assessment

There will be no benefit for subjects participating in this study. Given the observed pharmacological and toxicological profiles in nonclinical studies and previous clinical experience, it is judged that TC-5214 can be given in carefully monitored clinical trials.

The doses selected for subjects with moderate and severe renal impairment have been reduced to a single dose well below the highest single doses shown to be safe and well tolerated in healthy subjects.

Inclusion and exclusion criteria as well as study restrictions are chosen to ensure that the selected subjects are exposed to minimal risk.

The major risk for subjects who participate in the study is from AEs induced by TC-5214. The most likely safety concern for subjects receiving TC-5214 will be orthostatic hypotension, based on clinical data on mecamylamine and its mechanism of action. Orthostatic hypotension may occur when vascular volume is depleted, for example when fluid is withdrawn during the dialysis session. A low TC-5214 dose of 2 mg has been chosen for these subjects as an additional measure of safety.

There is a slight risk of infection or bruising that may occur as a result of phlebotomy. Treatment-emergent adverse events in the previous SAD study included vertigo, decreased neutrophil count, and somnolence in the TC-5214 4 mg group; vertigo in the TC 5214 8 mg group; nausea, xerosis, dizziness, eating disorder, and decreased appetite in the TC-5214 16 mg group. For further information regarding an overall risk benefit assessment, see [Investigator's Brochure TC-5214](#).

2. STUDY OBJECTIVES

2.1 Primary objective

To assess the pharmacokinetics of a single dose of TC-5214 in subjects with renal impairment and to compare the results with those in subjects with normal renal function

2.2 Secondary objectives

- To assess the effect of hemodialysis on TC-5214 PK
- To assess the safety and tolerability of TC-5214 in subjects with renal impairment compared with those subjects with normal renal function

2.3 Exploratory objectives

To collect samples for potential pharmacogenetic testing, which will allow future investigation of the influence of genotype on drug disposition and pharmacodynamic response

3. STUDY PLAN AND PROCEDURES

This Clinical Study Protocol has been subject to a peer review according to AstraZeneca standard procedures.

3.1 Overall study design and flow chart

This is a Phase I single dose, multi center, open-label study designed to evaluate the safety, tolerability and PK of TC-5214 in renally impaired subjects compared with subjects with normal renal function.

Based on an interim review of the safety and pharmacokinetics data, subjects with severe renal impairment (previous Group 4) will not be recruited for this study, and the study will be conducted in 2 parts.

Subjects will be enrolled into 1 of 4 groups in parallel, according to their degree of renal impairment based on their estimated glomerular filtration rate (eGFR), determined using the abbreviated, 4-variable Modification of Diet in Renal Disease (MDRD) formula as follows:

Group 1: control subjects with normal renal function: eGFR greater than 80 mL/min

Group 2: mild renal impairment: eGFR greater than or equal to 50 to 80 mL/min

Group 3: moderate renal impairment: eGFR greater than or equal to 30 to less than 50 mL/min

Group 5: end stage renal disease (ESRD): eGFR less than 30 mL/min, currently receiving dialysis

3.1.1 Part 1

3.1.1.1 Part 1, Groups 1 through 3

Subjects in Groups 1 through 3 will not be on dialysis. They will be admitted to the clinic the morning of Day -1, or on Day -2 at the discretion of the Investigator. Time-matched vital signs will be collected on Day -1. Subjects will then receive a single oral dose of TC-5214 on Day 1 and will remain in the clinic until the completion of the study assessments and procedures scheduled on Day 4. Subjects will return to the clinic for a follow-up visit 7 to 10 days following discharge from the clinic. Subjects in Group 1 who withdraw from the study prior to completion of all PK sample collections may be replaced; subjects in Groups 2 and 3 who withdraw from the study prior to completion of all PK sample collections may be replaced to ensure a minimum of 6 subjects complete the treatment period. During Part 1, subjects in Groups 1 through 3 will have pharmacokinetic blood and urine samples collected through 72 hours postdose.

3.1.1.2 Part 1, Group 5

The first 4 subjects enrolled into Group 5 will participate in 2 treatment periods, and receive a single oral dose of TC-5214 on each occasion. For Treatment Period 1 subjects will be

admitted into the clinic the morning of Day -1, or on Day -2 at the discretion of the Investigator. Time-matched vital signs will be collected on Day -1. Subjects will receive a single dose of TC-5214 on Day 1 after completion of a dialysis session and will remain in the clinic for pharmacokinetic sample collections and safety assessments until the start of their next dialysis session. Subjects who are unable to remain in the clinic during this time may have their samples collected as outpatients. Subjects will return to the clinic after a washout period of at least 2 weeks to start Treatment Period 2. Subjects will be admitted to the clinic the morning of Day -1 or on Day -2 at the discretion of the Investigator for Treatment Period 2. Time-matched vital signs will be collected on Day -1. Subjects in Treatment Period 2 will receive a single dose of TC-5214 on Day 1, at 4 hours prior to the start of a dialysis session. Subjects will remain in the clinic until the start of their next dialysis session. Blood samples will be collected prior to dialysis, during the entire dialysis session, and until the start of their next dialysis session. Safety assessments will be performed periodically throughout the treatment period. Dialysis fluid will be collected in 1-hour intervals. Subjects who are unable to remain in the clinic through the entire treatment period may have their samples collected as outpatients. Subjects will return to the clinic for a follow-up visit 7 to 10 days following discharge from Treatment Period 2. Subjects who withdraw from the study after completion of Treatment Period 1 (assessments between dialysis) and before entering Treatment Period 2 (assessments during dialysis) may be replaced at the discretion of the Sponsor.

For details on Part 1, see the Study Flow Charts ([Figure 1](#) and [Figure 2](#)) and the Study Plan Table 1 below.

3.1.2 Part 2

3.1.2.1 Part 2, Groups 1 through 3

Subjects in Groups 1 through 3 will not be on dialysis. They will be admitted to the clinic the morning of Day -1, or on Day -2 at the discretion of the Investigator. Time-matched vital signs will be collected on Day -1. Subjects will then receive a single oral dose of TC-5214 on Day 1 and will remain in the clinic until the completion of the study assessments and procedures scheduled on Day 6. Subjects will return to the clinic for a follow-up visit 7 to 10 days following discharge from the clinic. Subjects in Group 1 who withdraw from the study prior to completion of all PK sample collections may be replaced; subjects in Groups 2 and 3 who withdraw from the study prior to completion of all PK sample collections may be replaced to ensure a minimum of 6 subjects complete the treatment period.

During Part 2, subjects in Groups 1 through 3 will have blood and urine samples collected through 120 hours postdose.

3.1.2.2 Part 2, Group 5

The remainder of subjects enrolled into Group 5 will participate in 1 treatment period, and receive a single oral dose of TC-5214. They will be admitted to the clinic the morning of Day -1, or on Day -2 at the discretion of the Investigator. Time-matched vital signs will be collected on Day -1. Subjects will then receive a single oral dose of TC-5214 on Day 1 after

completion of their first inpatient dialysis session, and will remain in the clinic until the completion of the study assessments and procedures scheduled on Day 6.

[figure not shown]
Pharmacokinetic blood samples will be collected after a single oral dose (Day 1) for up to 120 hours postdose. Samples will be collected through 72 hours postdose (assessment between dialysis) and between 72 and 120 hours (assessment during dialysis).

Pharmacokinetic urine samples will be collected for up to 120 hours postdose from subjects who are able to produce urine.

Subjects will return to the clinic for a follow-up visit 7 to 10 days following discharge from the clinic. Subjects who withdraw from the study prior to completion of all pharmacokinetic sample collections may be replaced at the discretion of the Sponsor.

For details on Part 2 see the Study Flow Charts ([Figure 1](#) and [Figure 3](#)) and the Study Plan [Table 2](#) below.

Figure 1: Study Flow Chart Groups 1 through 3

[figure not shown]
^a Visit 1 may be conducted over 1 or more days during the screening period.

^b A single dose of TC-5214 8 mg will be administered for Groups 1 and 2, 2 mg will be administered for Groups 3 on Day 1.

^c Subjects may be admitted to the clinic on Day -2 to allow for the Day 1 time-matched safety assessments at the discretion of the Investigator.

[figure not shown]
^d For subjects in Groups 1 through 3, during Part 1 blood and urine samples are collected through 72 hours postdose, and for Part 2, blood and urine samples are collected through 120 hours postdose.

Figure 2: Study Flow Chart Group 5, Part 1

- ^a Visit 1 may be conducted over 1 or more days during the screening period.
- ^b A single dose of TC-5214 2 mg will be administered to Group 5 on Day 1 of each residential period
- ^c Subjects may be admitted to the clinic on Day -2 to allow for the Day 1 time-matched safety assessments at the discretion of the Investigator.
- ^d At least 14 days between TC-5214 administrations.

Figure 3: Study Flow Chart Group 5, Part 2

- ^a Visit 1 may be conducted over 1 or more days during the screening period.
- ^b A single dose of TC-5214 2 mg will be administered to Group 5 on Day 1.
- ^c Subjects may be admitted to the clinic on Day -2 to allow for the Day 1 time-matched safety assessments at the discretion of the Investigator.

Table 1: Study Plan, Part 1

Visit number	1	2 Residential Period (For Group 5, Part 1 – 2 Residential Periods)					3		
	Activity/ Day	-30 to -2 Screening	-1 ^h	1	2	3	4	Follow-Up 7 to 10 days following discharge	Details in Section
Informed consent	X								8.4
Demography	X								6.2
Inclusion/exclusion criteria	X	X							4
Physical Examination	X	X ⁱ					X ⁱ	X	6.3.6
Height and weight ^a	X	X					X		6.3.6
Medical and Surgical History	X								6.2
Columbia Suicide Severity Rating Scale	X	X					X	X	6.2
Clinical chemistry	X	X					X	X	6.3.5
Hematology	X	X					X	X	6.3.5
Urinalysis	X	X					X	X	6.3.5
HIV and HBV Serology	X								6.3.5
Drugs of Abuse Screen	X	X							6.3.5
Alcohol Screen		X							6.3.5

Visit number	1	2 Residential Period (For Group 5, Part 1 – 2 Residential Periods)					3		
	Activity/ Day	-30 to -2 Screening	-1 ^h	1	2	3	4	Follow-Up 7 to 10 days following discharge	Details in Section
Blood pregnancy test for female subjects of childbearing potential	X	X					X		6.3.5
Orthostatic blood pressure (supine, seated, and standing) and pulse ^b	X	X	X	X	X	X	X	X	6.3.7
Oral temperature and respiration rate	X	X	X	X	X	X	X	X	6.3.5
12-lead ECG ^c	X	X	X				X	X	6.3.6.1
Admission to the clinic		X							NA
Pharmacogenetic sampling (optional) ^k		X							6.5.1
TC-5214 administration ^d			X						5.5.2
Blood sample collection for PK ^e			X	X	X	X	X		6.4.1.1
Urine sample collection for PK ^f			X	X	X	X	X		6.4.1.2
Dialysis Period / Dialysate Collection			X ^j						6.4.1.4
Discharge from clinic							X ^g		NA

Visit number	1	2 Residential Period (For Group 5, Part 1 – 2 Residential Periods)					3		
	Activity/ Day	-30 to -2 Screening	-1 ^h	1	2	3	4	Follow-Up 7 to 10 days following discharge	Details in Section
Concomitant medications	X	X	X	X	X	X	X		5.6
Adverse Events	X	X	X	X	X	X	X		6.3

^a Height will be measured during the screening visit only.

^b Orthostatic blood pressure and pulse will be measured at the Screening Visit, on Day -1 (time to correspond with the planned predose and 4 hour postdose timings for Day 1), on Day 1 at predose and 4 hours post dose, each morning during the residential period and at the Follow-up Visit.

^c Subjects must rest in the supine position for 10 minutes prior to the 12-lead ECG evaluation to be performed at screening, on admission on Day -1, on Day 1 at 4 hours postdose, before discharge on Day 4, and at the Follow-up Visit

^d Study drug will be administered with 240 mL room temperature water

^e For detailed timings of blood PK sampling times see Section 6.4.1.1.

^f Urine collection times for Groups 1 to 3: Urine will be collected for 72 hours postdose in the following intervals: 0-12, 12-24, 24-48 and 48-72 hours.

^g Subjects will be discharged from the unit after all study procedures have been completed.

^h Subjects may be admitted to the clinic on Day -2 for the Day -1 assessments at the discretion of the Investigator.

ⁱ Abbreviated physical examination.

^j Applies only to Group 5, Part 1, Treatment Period 2. Subjects will start their scheduled dialysis at 4 hours post TC-5214 administration. Dialysate will be collected over 1 hour intervals throughout the entire (approximately 4 hour) dialysis session (eg, 0 to 1, 1 to 2, 2 to 3, and 3 to 4 hours).

^k Subjects must agree to sign a separate, optional informed consent for genetic research in order for this sample to be collected.

Table 2: Study Plan, Part 2

Visit number	1	2 Residential Period							3	
	-30 to -2 Screening	-1 ^h	1	2	3	4	5	6	Follow-Up 7 to 10 days following discharge	Details in Section
Informed consent	X									8.4
Demography	X									6.2
Inclusion/exclusion criteria	X	X								4
Physical Examination	X	X ⁱ						X ⁱ	X	6.3.6
Height and weight ^a	X	X						X		6.3.6
Medical and Surgical History	X									6.2
Columbia Suicide Severity Rating Scale	X	X						X	X	6.2
Clinical chemistry	X	X						X	X	6.3.5
Hematology	X	X						X	X	6.3.5
Urinalysis	X	X						X	X	6.3.5
HIV and HBV Serology	X									6.3.5
Drugs of Abuse Screen	X	X								6.3.5
Alcohol Screen		X								6.3.5
Blood pregnancy test for female subjects of childbearing potential	X	X						X		6.3.5

Visit number	1	2 Residential Period							3	
Activity/ Day	-30 to -2 Screening	-1^h	1	2	3	4	5	6	Follow-Up 7 to 10 days following discharge	Details in Section
Orthostatic blood pressure (supine, seated, and standing) and pulse ^b	X	X	X	X	X	X	X	X	X	6.3.7
Oral temperature and respiration rate	X	X	X	X	X	X	X	X	X	6.3.5
12-lead ECG ^c	X	X	X					X	X	6.3.6.1
Admission to the clinic		X								NA
Pharmacogenetic sampling (optional) ^j		X								6.5.1
TC-5214 administration ^d			X							5.5.2
Blood sample collection for PK ^e			X	X	X	X	X	X		6.4.1.1
Urine sample collection for PK ^f			X	X	X	X	X	X		6.4.1.2
Dialysis Period			X			X				6.4.1.4
Dialysate Collection						X ^j				6.4.1.4
Discharge from clinic								X ^g		NA
Concomitant medications	X	X	X	X	X	X	X	X		5.6
Adverse Events	X	X	X	X	X	X	X	X	X	6.3

- a Height will be measured during the screening visit only.
- b Orthostatic blood pressure and pulse will be measured at the Screening Visit, on Day -1 (time to correspond with the planned predose and 4 hour postdose timings for Day 1), on Day 1 at predose and 4 hours postdose, each morning during the residential period and at the Follow-up Visit.
- c Subjects must rest in the supine position for 10 minutes prior to the 12-lead ECG evaluation to be performed at screening, on admission on Day -1, on Day 1 at 4 hours postdose, before discharge on Day 6, and at the Follow-up Visit.
- d Study drug will be administered with 240 mL room temperature water.
- e For detailed timings of blood PK sampling times see Section 6.4.1.1.
- f Urine collection times: Urine samples for PK will be collected for 120 hours postdose in the following intervals: 0-12, 12-24, 24-48, 48-72, 72-96, and 96-120 hours. Urine will be collected for subjects in Part 2 for Groups 1 through 3, and for subjects in Group 5 who produce urine.
- g Subjects will be discharged from the unit after all study procedures have been completed.
- h Subjects may be admitted to the clinic on Day -2 for the Day -1 assessments at the discretion of the Investigator.
- i Abbreviated physical examination.
- j For Group 5 (Part 2), dialysate will be collected over 1 hour intervals throughout the entire (approximately 4 hour) dialysis session (eg, 72 to 73, 73 to 74, 74 to 75, and 75 to 76 hours postdose).
- k Subjects must agree to sign a separate, optional informed consent for genetic research in order for this sample to be collected.

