3.2 Rationale for study design, doses and control groups

The purpose of this study is to determine if renal impairment will affect the PK of TC-5214. The study is designed using the principals embodied in the Food and Drug administration guidance on drug renal impairment studies ([Cockcroft 1976](#)).

For control subjects with normal renal function and subjects with mild renal impairment, a 8 mg dose of TC-5214 was chosen because it is the highest daily dose that will be administered in Phase III trials and was shown to be well tolerated in healthy subjects in previous studies. For subjects with moderate and severe renal impairment, to minimize the effects of compensatory changes such as significant hypotension, a 2 mg dose will be administered.

In order to avoid bias due to demographic differences between the control subjects with normal renal function and subjects with renal impairment, the control group will be matched to the mean demographic characteristics of the **3** renal impairment groups with an allowable variability in age of +/- 10 years and in BMI of $\pm 3 \text{ kg/m}^2$. Sex will be matched to achieve similar distribution between male and female subjects. Only control subjects with stable chronic medical conditions will be included.

Based on available data to date, the mean terminal half-life ($t_{1/2,\lambda_z}$) of TC-5214 in human plasma is approximately 8 to 9 hours. Based on limited interim PK data in 2 subjects with moderate impairment, and 2 subjects with ESRD, renal impairment has been shown to increase the half-life of TC-5214 by approximately 3 and 10 fold, respectively.

For Groups 1 to 3, the study design has been updated to extend the sampling period to 120 hours postdose to adequately characterize the elimination phase of TC-5214 and more accurately determine TC-5214 PK parameters (eg $t_{1/2,\lambda_z}$, AUC, and CL/F). For Group 5 it was determined that a single dose of TC-5214 administered after the completion of a dialysis session, with the collection of blood samples for PK through 120 hours postdose (including a 4 hour dialysis session beginning approximately 72 hours postdose) would enhance patient safety.

The PK profile in patients with severe renal failure will be extrapolated from the data in subjects on dialysis obtained between their dialysis sessions, thus subjects with severe renal impairment (eGFR <30 mL/min) will not be recruited for this study.

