6.3.7 Vital signs

For timing of individual measurements refer to study plans [Table 1](#) and [Table 2](#).

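### Group 5: no orthostatic reading is scheduled between the end of the on-drug dialysis session and the next morning, though Section 1.4 cites dialysis fluid loss as its example of the risk

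*Supplement*

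**What the plan says.** Section 1.4 ranks orthostatic hypotension first among the expected safety concerns and adds: "Orthostatic hypotension may occur when vascular volume is depleted, for example when fluid is withdrawn during the dialysis session". The response given there is the 2 mg dose.

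Section 6.3.7 sets no times itself: "For timing of individual measurements refer to study plans" (Tables 1 and 2). Footnote b of Table 2 places three-position blood pressure and pulse at screening, at matched times on Day -1, and then "on Day 1 at predose and 4 hours postdose, each morning during the residential period and at the Follow-up Visit". Footnote b of Table 1 gives Part 1 the same schedule: "on Day 1 at predose and 4 hours post dose, each morning during the residential period", plus follow-up. Neither table has a separate orthostatic schedule for Group 5.

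Dialysis while on drug falls as follows:

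- **Part 1, Period 2.** Table 1, footnote j: "Subjects will start their scheduled dialysis at 4 hours post TC-5214 administration". Section 6.4.1.1 ties the 8 h blood sample to the end of that session. Section 3.1.1.2 adds only "Safety assessments will be performed periodically throughout the treatment period".
- **Part 2.** Under Section 3.1.2.2 the dose follows "completion of their first inpatient dialysis session, and will remain in the clinic" through Day 6. The next session runs from about 72 to 76 h postdose, on Day 4. Section 3.2 presents the Part 2 schedule as a safety gain: "including a 4 hour dialysis session beginning approximately 72 hours postdose) would enhance patient safety".

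**The concern.** The protocol names the situation in which its main safety concern is likely to appear, yet the schedule takes no standing reading there. Other afternoons and evenings on drug also go without readings, but this is the one the protocol itself picks out.

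The other safety provisions do not clearly fill the gap:

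- The Part 1 text on periodic assessments names no test and no time, and Part 2 has no such sentence.
- Under Section 6.3.3, a worsened protocol-mandated vital sign becomes an adverse event only if it meets serious criteria, leads to discontinuation, or the investigator chooses to report it.
- Under Section 12.2.2, unscheduled readings are listed but kept out of the descriptive statistics.
- The review for other significant adverse events (Section 11.1.1) can look only at data that were collected.

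What is at stake is the safety of a volume-depleted subject getting up with drug still on board, and a usable description of tolerability within ESRD. No pharmacokinetic endpoint and no comparison with controls depends on this.

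**Working it through.** The plan states no figure to reproduce. The check lays the reading times against the dialysis windows, then asks how long the gap is and how much drug is present.

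**1. Reading times against sessions**

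| Setting | On-drug session | Last scheduled reading before the session ends | Next scheduled reading |
|---|---|---|---|
| Part 1, Period 2 | about 4 to 8 h, Day 1 | Day 1, 4 h, at the start of dialysis | Day 2 morning |
| Part 2 | about 72 to 76 h, Day 4 | Day 4 morning | Day 5 morning |

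The Part 2 row assumes that the Day 4 morning reading comes before the session ends. Since 72 h is three whole days, the Day 4 session starts at the clock time of the dose. For it to end by noon, dosing must be by 12:00 − 4 h = 08:00. The Day 1 session of about 4 h must then start by about 04:00. That is unlikely.

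**2. Length of the gap** (clock times are assumptions; morning reading at 06:00 to 08:00)

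- Part 2, session end = dose time + 4 h on Day 4. Dose at 12:00: end 16:00, gap 14 to 16 h. Dose at 16:00: end 20:00, gap 10 to 12 h.
- Part 1 Period 2, session end = dose time + 8 h on Day 1. Dose at 08:00: end 16:00, gap 14 to 16 h. Dose at 12:00: end 20:00, gap 10 to 12 h.

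Both give 10 to 16 h. Wider assumptions, with morning readings at 06:00 to 10:00, give:

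- Part 1 Period 2: dosing at 07:00 to 12:00, gap 10 to 19 h.
- Part 2: Day 1 dialysis starting at 05:00 to 08:00 and dosing 0 to 2 h after it ends, gap 12 to 21 h.

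**3. Drug remaining**

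Section 3.2 gives a usual half-life of 8 to 9 h and about a tenfold increase in ESRD (2 subjects), hence 80 to 90 h. Fraction of the post-absorption level left = 0.5^(t / half-life), ignoring removal by dialysis:

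| Time postdose | Half-life 80 h | Half-life 90 h |
|---|---|---|
| 4 h | 0.966 | 0.970 |
| 8 h | 0.933 | 0.940 |
| 76 h | 0.518 | 0.557 |

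**4. Does the Day 1, 4 h reading stand in?**

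Only in part. In Part 2 and in Part 1 Period 1 it is on drug and after dialysis, but that fluid was removed before the dose. In Part 1 Period 2 it falls at the start of dialysis, before fluid is removed.

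**5. Who is affected**

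Amendment 1 counts 4 ESRD subjects still to be studied. Part 1 Period 2 applies only to the first 4 Group 5 subjects, and the documents do not say whether any of those sessions are outstanding.

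**The case against.** The strongest reply is that the protocol already answers the risk it names. It cuts the dose to 2 mg, and Part 2 moves on-drug dialysis from 4 h to about 72 h. If the dose is fully absorbed, 52 to 56% of 2 mg is about 1.0 to 1.1 mg. Section 13.2 reports single doses up to 16 mg as well tolerated in healthy subjects, and Section 1.1 says racemic mecamylamine at 2.5 to 10 mg/day does not affect blood pressure. The Day 1, 4 h reading in Part 2 is taken after dialysis at about 97% of the post-absorption level and has a matched Day -1 baseline. Section 5.1 keeps subjects sitting or semi-recumbent for 4 h after dosing. Symptomatic falls would be caught by adverse event collection. The proposed reading has no matched baseline and cannot separate drug from dialysis.

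Much of this stands, and it lowers the priority. It does not close the gap. The tolerability data are not from ESRD, and TC-5214 is the more active enantiomer. The posture rule lapses before either on-drug session ends. Exclusion 25 lets renal subjects on beta blockers, vasodilators or calcium channel blockers enrol at the investigator's discretion, with dose reduction only a possibility; controls may not take these drugs. Checking standing pressure before a just-dialysed subject walks is useful whatever the cause of a fall.

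**Conclusion.** The concern holds. No orthostatic reading is scheduled between the end of the on-drug dialysis session and the next morning, in either part. Without such a reading, a fall that causes no symptoms would go undetected unless staff chose to measure.

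The absence of a reading follows from the tables, given that the Part 2 session does not end before the Day 4 morning reading. The length of the gap rests wholly on assumed clock times. The exposure figures rest on a half-life from 2 subjects and ignore dialytic clearance, so true levels after dialysis are lower. Priority is minor to moderate: few subjects are affected, the remaining sessions are mostly or all in the lower-exposure setting, and no analysis changes.

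**What to change.** In Table 2, footnote b, add for Group 5 one supine, seated and standing blood pressure and pulse set directly after the 76 h blood draw. Add the same to Table 1 after the 8 h draw in Part 1 Period 2, if that period is still open. State it as an exception to the Section 6 order, which puts blood pressure before the blood sample, because the 76 h and 8 h samples must be drawn as soon as dialysis ends. List it as a scheduled assessment so that it enters the Section 12.2.2 summaries.

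**Cost.** Section 6.3.7.1 implies 10 + 2 + 3 = 15 minutes per session, so 15 × 4 = 60 minutes over the 4 remaining subjects. Staff are already present for the draw. It needs one extra CRF line and no invasive procedure.

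**Limits.** The reading asks a just-dialysed subject to stand for 3 minutes. It has no Day -1 matched baseline and no counterpart in Groups 1 to 3, so it should be reported as a description within Group 5, without attributing a fall to drug rather than dialysis.
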